5.1.4 Vaccine Distribution Procedures

Based on prior annual influenza vaccine use, we anticipate that KPNC will administer influenza vaccines to approximately 800,000 individuals aged 18–64 years, including 350,000 persons aged 50–64 years each season.

Approximately 400,000 doses of Flublok Quadrivalent vaccine and 400,000 doses of comparator SD-IIV will be administered to adults aged 18–64 years in each of the influenza seasons 2018–2019, 2019–2020, and 2020–2021.

There are approximately 70 facilities that receive individual influenza vaccine shipments from the KPNC Central Pharmacy (the exact number varies slightly each year; see **Figure 2** for an example of the flow). KPNC Central Pharmacy begins “autoshipments” to the Medical Centers and their satellite facilities’ main pharmacies in August in preparation for annual influenza vaccination clinics. For purposes of this study, medical center facilities include all associated satellite sites. KPNC Central Pharmacy determines the amount of vaccines to be shipped each day to the medical center facilities based upon vaccine use the previous year at each facility. For example, since Oakland Medical Center administered ~5% of all vaccines during the 2017–2018 influenza season, they would receive 5% of the daily shipment of vaccines during the subsequent 2018–2019 influenza season. Facilities may also request additional vaccine as needed.

Figure 2. Influenza Vaccine Distribution Flowchart Example

Once the facilities receive adequate influenza vaccines to distribute to all of their influenza vaccination clinics, they will prepare vaccine allotments for specific patient populations within each clinic (e.g., adult medicine, OB/GYN). We propose to randomize these facilities to distribute (and therefore administer) either Flublok Quadrivalent vaccine or a SD-IIV initially to all of their influenza vaccination clinics. Roughly half the facilities will first distribute Flublok Quadrivalent vaccine to be administered by their associated departments and clinics, while the other half will first distribute a SD-IIV for administration by their associated departments and clinics. The facilities will follow a weekly alternating schedule (with some variation due to usage) that indicates which vaccine is to be internally distributed to associated departments and clinics for the entire influenza season. Historically, >75% of vaccinations to adults aged 18–64 are administered prior to Thanksgiving.

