In particular, we will emphasize that the injection nurse administering the vaccine should not preferentially choose one vaccine over the other, but instead use what is available in the refrigerator or portable cold storage box for the day. Based on routine influenza clinic operations, there is little potential for bias at the level of vaccine administration level (e.g., an injection nurse preferentially choosing one vaccine over the other), especially early in the season, when large numbers of influenza vaccine are administered on any given day; injection nurses are unlikely to spend time searching for a specific formulation based on preference. Further, by following the alternating vaccine supply schedule, we will reduce the likelihood that both Flublok Quadrivalent vaccine and SD-IIV are simultaneously available in the clinic. By having only one vaccine available for adults aged 18–64 years (Flublok Quadrivalent vaccine or SD-IIV), we hope to reduce the likelihood that an injection nurse is able to choose one vaccine over the other.

Because influenza vaccine is used at a very rapid pace once influenza clinics officially begin administering vaccine, the departments and clinics may request vaccine replenishment prior to the next distribution in order to ensure adequate supply. For this reason, it may be possible that a particular clinic will have both Flublok Quadrivalent vaccine and a SD-IIV available.

On a weekly basis, we will also monitor both the distribution of vaccine from KPNC Central Pharmacy to the facility pharmacies, as well as influenza vaccine administration. If we detect imbalances at either of these points, we will work closely with the affected facility(s) to attempt to correct the imbalance. Additional details may be found in Section 11.1.

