6.5 Randomization and Allocation Procedures

Subjects will not be individually randomized. A modified-cluster randomization scheme by facility will be deployed.

This study will employ a design whereby KPVSC will ensure that all clinics in KPNC will receive alternating distribution of Flublok Quadrivalent vaccine or SD-IIV. All KPNC facilities will follow a schedule that alternates which vaccine is supplied to each influenza clinic throughout the 3-year season period.

We will block facilities and randomize within blocks (see **Section 5.1.4**), ensuring that roughly half the facilities within each block initially administer Flublok Quadrivalent vaccine and the other half administer a SD-IIV. After the initial supply, the half that started with Flublok Quadrivalent vaccine will be supplied with the SD-IIV, and the half that started with SD-IIV will be supplied with Flublok Quadrivalent vaccine (see **Figure 1**). The supply of each clinic will then alternate between the two vaccines; that is, Flublok Quadrivalent vaccine alternating with SD-IIV with each delivery of vaccine to the clinics.

Figure 1: Visual of block randomization influenza vaccine administration schedule			
	Week 1	Week 2	Week 3
Block A			
Facility 1			
Facility 3			
Facility 5	Flublok	Comparator IIV	Flublok
Facility 7			
Facility 9			
Block B			
Facility 2			
Facility 4			
Facility 6	Comparator IIV	Flublok	Comparator IIV
Facility 8			
Facility 10			

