11.1 Statistical Methods

Since we are not randomizing at the individual patient level, there is no vaccine being assigned to any patient. The intent is to balance Flublok versus SD-IIV comparisons by balancing the shipments and delivery of the vaccines by clinic and calendar week.

The preliminary analyses will compare the incidence of each of the outcomes in Flublok Quadrivalent vaccinees versus SD-IIV vaccinees. We plan to test the null hypothesis that Flublok is not any more effective than the comparator (i.e., a superiority test), using a 2-sided test, $p<0.05$. The primary analyses will use Cox regression to obtain an adjusted estimate of the relative hazard ratio (rHR) for each outcome, adjusted for age, sex, race/ethnicity, facility, and time-since-vaccination. The rHR at any point in the follow-up period is the instantaneous relative risk (RR) at that time (i.e., we are estimating rVE by $(1-rHR)$, and testing the null hypothesis that $rHR=0$). In addition, we may adjust for an available comorbidity score and/or a measure of prior exposure to influenza vaccines (e.g., exposure to flu vaccine in the prior year, or number of flu shots in the past three years).

Risk sets will be conditioned (i.e., stratified) on calendar day, using a calendar timeline for the Cox regression. We expect many people to be vaccinated both years, and some might get “breakthrough” influenza both years. Getting Flublok in one year should be entirely unrelated to getting Flublok in another year, so robust standard errors are not needed. We will check our assumption that the vaccine received in one year is not related to vaccine received the next year. For each type of outcome, follow-up would end at the first outcome event in a season but could restart the next year when the individual is vaccinated again.

We do not know whether prior vaccination (i.e., booster or priming effect) affects VE of either Flublok Quadrivalent vaccine or SD-IIV, but we hypothesize that prior vaccination might be an effect modifier but not a potential confounder because what patients are vaccinated with in prior years should not be associated with what vaccine they receive in any of the 3 study seasons. We

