24	680,301	680,301	0.00065	0.95	0.05	0.12

Power of 3-yr study comparing FluBlok v Comparators
Power to detect relative VE against 5 types of outcome events
By age group (or chronic disease status) and outcome
2-sided alpha=0.05 (likelihood ratio chi-sq test for superiority)
800,000 vaccinees expected per yr: 400K fluBlok v. 400K comparators

age=50-64 outcome=flu, test+

row	N expectd 3 yrs FluBlok	N expectd 3 yrs Comprtr	proportion of comparators who have the outcome	RR = 1 minus relative VE	Relative VE: % of breakthru cases prevented	Power (prob. of rejecting Ho if rel_VE is true)
25	519,699	519,699	0.00205	0.70	0.30	>.99
26	519,699	519,699	0.00205	0.75	0.25	>.99
27	519,699	519,699	0.00205	0.80	0.20	>.99
28	519,699	519,699	0.00205	0.85	0.15	0.95
29	519,699	519,699	0.00205	0.90	0.10	0.66
30	519,699	519,699	0.00205	0.95	0.05	0.22

age=50-64 outcome=hosp, flutest+

row	N expectd 3 yrs FluBlok	N expectd 3 yrs Comprtr	proportion of comparators who have the outcome	RR = 1 minus relative VE	Relative VE: % of breakthru cases prevented	Power (prob. of rejecting Ho if rel_VE is true)
31	519,699	519,699	0.00120	0.70	0.30	>.99
32	519,699	519,699	0.00120	0.75	0.25	>.99
33	519,699	519,699	0.00120	0.80	0.20	0.96
34	519,699	519,699	0.00120	0.85	0.15	0.79
35	519,699	519,699	0.00120	0.90	0.10	0.44
36	519,699	519,699	0.00120	0.95	0.05	0.15

age=50-64 outcome=PneumoniaHosp,Dec-March

row	N expectd 3 yrs FluBlok	N expectd 3 yrs Comprtr	proportion of comparators who have the outcome	RR = 1 minus relative VE	Relative VE: % of breakthru cases prevented	Power (prob. of rejecting Ho if rel_VE is true)
37	519,699	519,699	0.00248	0.70	0.30	>.99
38	519,699	519,699	0.00248	0.75	0.25	>.99
39	519,699	519,699	0.00248	0.80	0.20	>.99
40	519,699	519,699	0.00248	0.85	0.15	0.98
41	519,699	519,699	0.00248	0.90	0.10	0.74
42	519,699	519,699	0.00248	0.95	0.05	0.25

Power of 3-yr study comparing FluBlok v Comparators
Power to detect relative VE against 5 types of outcome events
By age group (or chronic disease status) and outcome
2-sided alpha=0.05 (likelihood ratio chi-sq test for superiority)
800,000 vaccinees expected per yr: 400K fluBlok v. 400K comparators

age=50-64 outcome=CVD hosp, Dec-March

row	N expectd 3 yrs FluBlok	N expectd 3 yrs Comprtr	proportion of comparators who have the outcome	RR = 1 minus relative VE	Relative VE: % of breakthru cases prevented	Power (prob. of rejecting Ho if rel_VE is true)
43	519,699	519,699	0.00620	0.70	0.30	>.99
44	519,699	519,699	0.00620	0.75	0.25	>.99

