5.1.1.2 Statistical Methods

The primary, secondary, and exploratory analyses will use Cox regression on a calendar timeline to obtain an adjusted estimate of the relative hazard ratio (rHR) for each outcome, adjusted for age, sex, race/ethnicity, and facility or service area. The null hypothesis (that the $\log rHR = 0$) will be tested using the Wald test (based on the ratio of the adjusted $\log rHR$ estimate to its corresponding standard error estimate). The following covariates have been selected *a priori* to include in our model (via the propensity score, described further below):

- Age at time of vaccination (continuous)
- Sex
- Race (some small categories may be combined, if necessary):
 - White
 - Black
 - Asian
 - Pacific Islander
 - Native American
 - Multiracial
 - Unknown/Other
- Ethnicity:

- Hispanic
- Non-Hispanic/Unknown
- KPNC Facility or Service Area

In addition to estimating the rHR, conditional on the covariates above, we will consider whether the rVE of Flublok varies across subgroups or over time. For example, we may examine whether the rHR varies with:

- Time-since-vaccination: number of days, counting from Day 15 after vaccination (where day 0 is the day of vaccination)
- Time-since-beginning-of-the-season
- Season: Year 1, Year 2, or Year 3
- Comorbidities: Diagnostic cost groups (DxCG) risk scores from the ICD-based proprietary risk adjustment and predictive modeling system may be used. DxCG calculates projected healthcare costs for each member for the upcoming year based on demographics, diagnoses, costs, and utilization in the previous year. It may also be included as a proxy for overall health status of the individual.
- Prior healthcare utilization (e.g., number of emergency department visits or hospitalizations in prior year, outpatient visits in prior year)
- Influenza vaccine type received (or none) during the previous year

Adults who are included in our analysis must receive either Flublok or an SD-IIV. The majority of influenza vaccinations are administered in the KPNC region by the end of calendar year. It is possible that Flublok will not last until the end of the influenza season, which is typically in the spring of the following year, as determined by KPNC. Based on our alternating weekly schedule—one week of Flublok followed by one week of an SD-IIV—weeks are “paired” for balance.

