The following analyses will be conducted. The single-season analyses are for the purposes of assessing whether any season-specific considerations (or otherwise) need to be made for the overall analysis.

At the end of the third influenza season, we will assess:

- Single-season rVE against PCR-confirmed influenza (primary objective) based on data from the first influenza season (2018–2019)
- Single-season rVE against PCR-confirmed influenza (primary objective) based on data from the second influenza season (2019–2020)
- Single-season rVE against PCR-confirmed influenza (primary objective) based on data from the third influenza season (2020–2021)
- Potential single-season rVE against select secondary outcomes as feasible based on data from the first influenza season (2018–2019)

- Potential single-season rVE against select secondary outcomes as feasible based on data from the second influenza season (2019–2020)
- Potential single-season rVE against select secondary outcomes as feasible based on data from the third influenza season (2020–2021)

We expect that the featured analysis of rVE against each of the primary, secondary, and exploratory outcomes will be the overall analysis including all subgroups over both influenza seasons. If we find variation in rVE across subgroups and over time that is substantial, it will also be reported.

Risk sets will be conditioned (i.e., stratified) on calendar day, using a calendar timeline for the Cox regression. We expect many people to be vaccinated both years, and some might get “breakthrough” influenza both years. Getting Flublok in one year should be entirely unrelated to getting Flublok in another year, so robust standard errors are not needed. We will check our assumption that the vaccine received in one year is not related to vaccine received the next year. For each type of outcome, follow-up would end at the first outcome event in a season but could restart the next year when the individual is vaccinated again.

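### Robust standard errors are ruled out for a reason that covers one person across seasons, not people vaccinated together at one facility in one week, which is where vaccine type is set

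*SAP*

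**What the plan says.** Both documents carry the same sentence, in SAP 5.1.1.2 and Protocol 11.1: "Getting Flublok in one year should be entirely unrelated to getting Flublok in another year, so robust standard errors are not needed". The sentence just before it shows what it is about: "We expect many people to be vaccinated both years, and some might get “breakthrough” influenza both years". The check planned on the assumption also concerns vaccine type across years only.

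Vaccine type is set at another level. Protocol 6.5 says that individuals are not randomized and that "A modified-cluster randomization scheme by facility will be deployed". Protocol 5.1.4 adds: "The facilities will follow a weekly alternating schedule (with some variation due to usage"). Protocol 11.1 describes the aim in the same terms: "The intent is to balance Flublok versus SD-IIV comparisons by balancing the shipments and delivery of the vaccines by clinic and calendar week". Some mixing is expected, since with early replenishment "it may be possible that a particular clinic will have both Flublok Quadrivalent vaccine and a SD-IIV available".

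The Cox model is "adjusted for age, sex, race/ethnicity, and facility or service area" (SAP 5.1.1.2). It also conditions risk sets on calendar day and adjusts for a facility-specific propensity score. Neither document mentions an intracluster correlation, design effect, frailty term, cluster-robust variance or permutation test.

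**The concern.** Correlated outcomes bias a model-based standard error for a treatment contrast when the correlated people also share the treatment. The plan's sentence uses exactly this logic for repeat vaccinees: if one person's product in one season is unrelated to that person's product in the next, within-person correlation does little harm. The same logic points the other way for people vaccinated at one facility in one week, because they mostly do share a product.

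The planned adjustments, and the alternation of both products within each facility, remove stable facility differences and most variation from local epidemics (less if only service area is used). Two sources remain: unmeasured risk tied to facility and vaccination week, such as who attends in a given week, and variation in the vaccine effect between facilities.

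At stake are the primary Wald test and its 95% CI, over 2 × 519,699 = 1,039,398 person-seasons, the five Holm-adjusted secondary tests, and the stated power.

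**Working it through.** **1. Reproduce the stated power.** Inputs from the Protocol Section 15 tables (ages 50–64, PCR-positive influenza): n = 519,699 per arm, comparator proportion p0 = 0.00205, test described as "2-sided alpha=0.05 (likelihood ratio chi-sq test for superiority").

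λ = 2n[D(p0, p̄) + D(p1, p̄)], where p1 = p0·RR, p̄ = (p0 + p1)/2 and D(p, q) = p ln(p/q) + (1−p) ln((1−p)/(1−q)). Power = P(noncentral χ² with 1 df and noncentrality λ > 3.841).

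| rVE | λ | Computed | Stated |
|---|---|---|---|
| 20% | 23.77 | 0.998 | >.99 |
| 15% | 13.00 | 0.950 | 0.95 |
| 10% | 5.62 | 0.659 | 0.66 |
| 5% | 1.37 | 0.216 | 0.22 |

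The rows for hospitalized influenza, pneumonia and CVD hospitalization at ages 50–64 also reproduce within 0.01. The tables therefore use independent individuals and a design effect of 1.

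**2. Power under a design effect.** Divide λ by the design effect (DE). The DE values are assumptions.

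| DE | rVE 15% | rVE 10% | CI width factor (√DE) |
|---|---|---|---|
| 1.0 | 0.95 | 0.66 | 1.00 |
| 1.1 | 0.93 | 0.62 | 1.05 |
| 1.2 | 0.91 | 0.58 | 1.10 |
| 1.4 | 0.86 | 0.52 | 1.18 |

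The rVE detectable with 80% power moves from 11.8% at DE 1.0 to 12.3% at 1.1 and 13.8% at 1.4.

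**3. Analytic type I error.** DE = 1 + (m − 1)·ICC, with ICC = CV²·p/(1−p) and p = 0.00205. The unadjusted test then has error 2(1 − Φ(1.96/√DE)). With about 70 facilities (Protocol 5.1.4), 3 seasons and an assumed 20 vaccination weeks, mean facility-week size is 1,039,398/(70 × 3 × 20) = 247. An effective size of 495, about twice the mean, allows for unequal sizes. At CV 0.5, ICC = 0.25 × 0.00205/0.99795 = 0.000514, DE = 1 + 494 × 0.000514 = 1.25 and error = 8.0%. At CV 0.25, DE = 1.06 and error = 5.7%. At CV 0.1, DE = 1.01 and error = 5.1%.

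**4. Simulation under the null.** 12,000 runs per scenario, so Monte Carlo SE is about 0.2–0.3 points at the 5% level. Assumed structure: 70 unequal facilities (size CV 0.55), 3 seasons, 350,000 vaccinees aged 50–64 per season (Protocol 5.1.4), 28 weeks with 75% vaccinated in the first 10, weekly alternation from a random start, facility frailty SD 0.3, and gamma frailty by facility and vaccination week. The test was a score test conditional on facility and season, with either model-based variance or variance clustered on facility (t, 69 df).

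Type I error of the model-based test, primary outcome, nominal 5% (DE in brackets):

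| Facility-week CV | No mixing | 20% mixing |
|---|---|---|
| 0.1 | 5.0% (0.99) | 5.2% (1.02) |
| 0.25 | 5.7% (1.05) | 5.2% (1.04) |
| 0.5 | 7.3% (1.22) | 5.8% (1.06) |
| 0.7 | 9.9% (1.42) | 6.9% (1.17) |

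The facility-clustered test gave 4.1–4.7% throughout. A repeat with 3,000 fresh runs per cell agreed within Monte Carlo error.

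Model-based error at the first Holm threshold (nominal 1%), CV 0.25 / 0.5:

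| Outcome (appendix rate) | No mixing | 20% mixing |
|---|---|---|
| Hospitalized influenza (0.00120) | 1.0 / 1.6% | 1.1 / 1.2% |
| Pneumonia (0.00248) | 1.3 / 2.3% | 1.3 / 1.4% |
| CVD hospitalization (0.00620) | 1.6 / 4.6% | 1.3 / 2.0% |

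CVD hospitalization is the nearest row to the cardio-respiratory composite. Influenza A and B were not computed because no rates are given.

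**5. Vaccine effect varying between facilities.** With the log hazard ratio varying with SD 0.1 / 0.2 around a null average, the model-based test rejected in 6.5 / 12.9% of runs and the clustered test in 4.5 / 5.2%.

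**The case against.** The strongest reply is that the effect is small where it is plausible. A gamma frailty with CV 0.5 spans 0.27 to 2.19 (central 95%), an eight-fold range of residual risk between vaccination weeks at one facility; CV 0.7 spans about 22-fold. Nothing in the documents supports variation that large. About 2,130 events (1,039,398 × 0.00205) over 70 × 3 × 28 facility-weeks is roughly 0.36 per facility-week, which leaves clustering little to act on, and the expected mixing weakens it further. This stands, and is why no claim is made of material inflation at low CV.

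Second, the simulation omits calendar-day strata and the propensity score, which includes comorbidity and prior utilization and so adjusts measured case mix. This also stands: the CVs should be read as residual variation after those adjustments, and that residual is unknown. But adjusting for measured covariates does not make a model-based variance valid for what is unmeasured, and the SAP itself expects imbalances to remain.

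Third, the results in step 5 concern a null average effect, whereas the SAP's null is no difference in effectiveness. They should be read that way and not as type I error for a null of no effect at any facility.

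Fourth, power is hardly affected at larger effects. The protocol's rationale cites 30–43% greater efficacy in adults aged 50 and over; at rVE 25–30% power stays above 0.99 even at DE 1.4, and at 15% it remains above 80%. This is correct. Only smaller effects, such as 10%, lose noticeable power, and that row was already below 80%.

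These points limit the size of the problem. They do not supply the missing reason for excluding robust variance.

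**Conclusion.** The concern holds and should be fixed. The plan excludes robust standard errors on a reason that does not reach the level at which vaccine type is set. Overstated precision is possible but not demonstrated. For the primary outcome it is negligible at a facility-week CV of 0.1, small at 0.25, and clear only from about 0.5 (7.3% without mixing, 5.8% with 20% mixing). The largest Holm-threshold figure, 4.6% against a nominal 1%, needs CV 0.5, no mixing and a proxy outcome rate. All of these rest on assumed CVs, mixing, number of weeks and facility sizes, none of which the documents give. What needs no assumption is that the stated power treats individuals as independent. It is therefore an upper bound with respect to clustering; the incidence, taken from 2016–2017, is a separate assumption. Confidence is medium.

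**What to change.** Replace the sentence in SAP 5.1.1.2 and Protocol 11.1 with one to this effect: *All Wald tests and confidence intervals use a sandwich variance clustered on facility (about 70 clusters); model-based standard errors are shown for comparison.* State the reference distribution too; a t distribution with facilities minus one degrees of freedom was used in the simulations. Facility clusters contain the facility-weeks and also allow for between-facility variation in effect.

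Label the Section 15 power tables as assuming independent individuals, or show power over a stated range of design effects, for example 1.0 to 1.4.

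The cost is one sentence in each document, one option in the Cox procedure and a label on the tables. Intervals may be slightly wider and stated power slightly lower. The clustered test was slightly conservative in the simulations: 0.4–0.7% at the 1% threshold for the three Holm-family outcomes examined. If facility-week variation proves small, the two sets of standard errors will nearly agree, and showing both will document it.
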